4.0 Resources and Personnel

All study activities will occur at the SVAMC, in the SCI inpatient clinic.

Recruitment of subjects will be done by the PI, who will identify potentially eligible participants receiving SCI treatment at the SVAMC. Once potential subjects are identified, informed consent will be obtained by a research assistant or nurse. Only a nurse approved on the study will be responsible for collecting data.

5.0 Study Procedures

5.1 Study Design

Experiments will be conducted in the SCI inpatient clinic in 10 individuals with neurogenic bowel dysfunction who have stable bowel routines. We will work with nursing staff on the study to maintain a consistent bowel emptying schedule for the subjects. We will not disrupt the patient's typical bowel emptying routine. Only the Research Nurse will be completing any research related procedures. Data will be collected from subjects over 6 weeks during their typical bowel routines. Then we will test minimally invasive electrical rectal stimulation via a rectal probe in a second 6-week period. Subjects will be instrumented with a rectal probe and stimulator inserted by the Research Nurse only for the duration of those bowel routines and effects are not expected to continue past the end of the experiment period. Subjects will return to their typical bowel routine at the end of the 6-week stimulation testing period. For patients >6 months post-SCI, the control period for the study will consist of their typical digital stim bowel routine. Nurses will log dig stim data as they usually do and this data will be used as control data for the study. During the experimental phase of the experiment, dig stim will be replaced with electrical stimulation. Use of electrical stim will not change the patients' bowel routine otherwise. There is no set schedule for the intervention because we are adapting to each patients' normal bowel routine. The only structure is that we have a defined control period using their normal routine, followed by a defined experimental period with the electrical stimulation. For a normal bowel routine, patients typically receive bowel intervention every other day in a typical week.

For subjects within 6 months of SCI diagnosis, but after the acute spinal shock phase, we will instead alternate between periods of control intervention (dig stim) and electrical stimulation. This will be done 3-7 times a week to optimize data acquisition, rather than having a defined control period followed by a defined experimental period. Neither the altered procedure nor the inclusion of patients who are <6 months post-SCI will affect the risk level of the study. Acute spinal shock is defined as the period immediately following an acute spinal cord injury. This phase resolves 72 hours post-injury and it is exceptionally rare that a patient in this phase of injury would be in the SCI, rather than the ICU.

Typical Bowel Routine

Typical bowel routines usually involve digital rectal stimulation conducted by the subject, their nurse, or their caregiver. An individual inserts a gloved finger through the anus into the rectum and mechanically distends the rectum by moving back and forth against the inside of the rectal wall for approximately 30 seconds. Time is allowed for the colon to move and evacuate some stools, then the process is repeated (typically 15-20 minutes later). Digital rectal stimulation is thus repeated until the colon contents are empty, usually marked by the appearance of mucus and no evidence of stools in the distal colon or rectum. Some subjects may also receive a mini-enema or other

suppository to aid in bowel emptying. Individual bowel routine schedules vary but are typically conducted 3-5 times a week.

Electrical Rectal Stimulation

A clinically standard rectal probe electrode will be inserted into the rectum to administer electrical stimulation. The probe electrode will only be in place to administer bouts of stimulation just as gloved fingers administer digital rectal distension, after which it will be removed to allow for bowel emptying. The probe electrode will be connected to a Digitimer stimulator DS7A, which is FDA-approved for electrical stimulation in human subjects and has been used in our previous, similar experiments for bladder function. Stimulation will either be 20 Hz constant frequency or burst pattern stimulation delivered as 5-50 pulses at 100-200 Hz once per second. We will first determine the stimulation amplitudes at which the subject can sense stimulation and at what limit they tolerate stimulation but do not wish to go higher for concern of discomfort. We will then apply stimulation within this range, not expected to exceed 40 mA, which is the typical range we see in similar applications of surface electrical stimulation. Stimulation will be administered continuously for the duration of the bowel routine. If stimulation does not increase colonic motility and promote defecation, as determined by each subject's baseline data on bowel emptying time, nurse experience, or clinician expertise, then we will cease stimulation for that day and return to the subject's typical bowel routine. If stimulation fails to increase colonic motility for bowel emptying on 3 or more occasions in a given subject, then we will stop the 6-week stimulation period and return that subject to their typical bowel routine.

The procedures in this study involve certain risks, which are similar to the risks of digital rectal stimulation, which is part of a participant's bowel routine. The incremental risks involved in performance of these studies are not significantly greater than those encountered during a standard bowel routine. However, these risks are outlined in the participant's consent form, along with explanations of what would be done to reduce the likelihood of adverse events, and what would be done should any occur.

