Electrical stimulation to evoke recto-colonic reflex for colonic motility

Funding Agency: VA RR&D

Principal Investigator: [name], DO

1593201-8/12-3-21/2021

Abstract

This study hopes to characterize the effects of minimally invasive electrical rectal stimulation on colonic motility in persons with neurogenic bowel dysfunction. Subjects will act as their own controls, with control data being obtained during subjects' typical bowel routines. Outcome measures include bowel emptying duration and amount of stool removed. These data will be compared to determine the efficacy of electrical stimulation to promote bowel emptying compared to patients' typical bowel routines, and to provide an effect size on the outcome measures of colonic motility for powering future studies.

We hypothesize that electrical rectal stimulation will produce increased colonic motility that results in defecation and that defecation time will be similar to subjects' typical bowel routines. The time required for defecation in response to their typical bowel routine and to minimally invasive electrical rectal stimulation will be monitored. Subjects will also be asked to report on sensations and comment on electrical stimulation.

List of Abbreviations

LSCDVAMC: Louis Stokes Cleveland DVA Medical Center

SVAMC: Syracuse VA Medical Center

SCI: spinal cord injury

EMG: electromyogram

AD: autonomic dysreflexia

NBD: neurogenic bowel dysfunction

FES: functional electrical stimulation

IRB: Institutional Review Board

Contents

1.0	Study Personnel	5
2.0	Introduction	5
3.0	Objectives	6
4.0	Resources and Personnel	6
5.0	Study Procedures	7
5.1	Study Design.....	7
5.2	Recruitment Methods	8
5.3	Informed Consent Procedures	9
5.4	Inclusion/Exclusion Criteria	9
5.5	Study Evaluations	10
5.6	Data Analysis.....	10
5.7	Withdrawal of Subjects	11
6.0	Reporting.....	11
7.0	Privacy and Confidentiality.....	11
8.0	References	12

Protocol Title: Electrical stimulation to evoke recto-colonic reflex for colonic motility

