5.6 Data Analysis

This work is considered a pilot study. Data will be collected to determine an effect size and power future studies that measure colonic motility in response to electrical stimulation. Therefore, 10 subjects are chosen to provide sufficient data to power a future study.

Bowel emptying will be performed by a trained clinician, caregiver, or subject (whoever normally performs it for the subject) using standard technique. The bowel routine is typically conducted with digital rectal stimulation and/or the insertion of suppositories or similar chemical systems. The time that elapses between initial intervention and bowel emptying will be measured as bowel emptying time. We will also test electrical stimulation to modulate an excitatory recto-colic reflex by stimulating via a rectal probe electrode. These systems are clinically available for chronic constipation in other indications and are considered minimal risk. We have experience measuring bowel activity with these methods. Initial introduction of the rectal probe electrode may cause temporary distension of the rectum. To ensure that reflexive activity due to the probe does not confound our data, we will wait approximately 5-10 minutes for the colon to relax back to baseline activity before beginning the bowel routine with stimulation.

The primary outcome variable is bowel emptying time. Bowel emptying time data are not expected to follow a normal distribution. Therefore, the non-parametric Mann-Whitney rank-sum test with a significance of 0.05 will be used to compare bowel emptying times between typical bowel routines and electrical stimulation conditions

across subjects. We expect to observe a great deal of variability in bowel emptying times, which may require many observations and subjects to achieve statistical significance.

Analysis on de-identified data will be performed by study staff. De-Identified data from this study may be pooled with data collected by [name] originating from a similar study of the same name currently approved at the Louis Stokes Cleveland DVA Medical Center.

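### Section 5.6 plans an unpaired Mann-Whitney test for own-control data and leaves the unit unstated, while the three-failure stop makes each subject's share of stimulation sessions depend on response.

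*Combined protocol and SAP*

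**What the plan says.** - **Design.** The Abstract states: "Subjects will act as their own controls". Under section 5.1, subjects more than 6 months after injury have 6 control weeks and then 6 stimulation weeks. More recently injured subjects alternate conditions "rather than having a defined control period followed by a defined experimental period".
- **Failed session.** Section 5.1 (Electrical Rectal Stimulation) returns an ineffective session to the usual routine: "as determined by each subject's baseline data on bowel emptying time, nurse experience, or clinician expertise, then we will cease stimulation for that day". No numerical threshold is given.
- **Subject-level stop.** The stimulation period ends if stimulation "fails to increase colonic motility for bowel emptying on 3 or more occasions in a given subject, then we will stop". Control sessions have no matching rule.
- **Outcome.** Section 5.6: "The time that elapses between initial intervention and bowel emptying will be measured as bowel emptying time". Reverted sessions are not mentioned. Read literally, they are timed through to emptying, fallback included.
- **Test.** A Mann-Whitney rank-sum test at 0.05 "will be used to compare bowel emptying times between typical bowel routines and electrical stimulation conditions", across subjects. Whether sessions or subject summaries are ranked is not stated. The nearest hint is: "We expect to observe a great deal of variability in bowel emptying times, which may require many observations and subjects to achieve statistical significance".
- **Purpose.** "Data will be collected to determine an effect size and power future studies that measure colonic motility in response to electrical stimulation".

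**The concern.** The design is paired and the test is not. The stop also makes the amount of stimulation data depend on the outcome being analysed. If sessions are ranked together, subjects who do badly on stimulation supply few stimulation sessions but a full set of control sessions, and repeated sessions from one person are treated as independent. If one summary per subject and condition is ranked, the weighting problem largely goes, but differences between subjects enter as noise that the design was meant to remove.

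The pilot's product is an effect size for planning later work, and its stated hypothesis is that emptying times are similar. A shifted estimate would misplan the next study. A non-significant result from an insensitive test could be read as support for similarity.

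**Working it through.** **The plan's own figure.** The sample size is 10. No SD, effect size or power is given, so it cannot be reproduced. Every variance and cut-off below is assumed.

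**Step 1: session counts, which need no variance.** Every other day for 6 weeks is 42/2 = 21 sessions per condition (section 5.1). With per-session failure risk f and a stop at the third failure, expected stimulation sessions are the sum over t = 0 to 20 of P(Binomial(t, f) ≤ 2). The chance of stopping before session 21 is P(Binomial(20, f) ≥ 3).

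| f | 5% | 10% | 20% | 30% | 50% | 100% |
|---|---|---|---|---|---|---|
| Expected stimulation sessions | 20.5 | 18.8 | 13.8 | 9.9 | 6.0 | 3.0 |
| P(early stop) | 0.08 | 0.32 | 0.79 | 0.96 | 1.00 | 1.00 |

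A consistent non-responder therefore gives 3 stimulation sessions against 21 control sessions. At 3-5 routines a week (18-30 sessions) it is 3 against 18 to 3 against 30.

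**Step 2: pooled sessions, simulated.** The model is log time = subject baseline (SD 0.4) + response under stimulation (mean 0, SD r, independent of baseline) + session error (SD 0.4). There are 10 subjects with 21 control and up to 21 stimulation sessions each. A stimulation session fails if its time exceeds 1.5x or 2x the subject's control median. Its recorded time is then the cut time plus a fresh usual-routine time. The test is two-sided Mann-Whitney at 0.05; the plan does not state sidedness. Entries are the percentage of trials significantly favouring/opposing stimulation when the average effect is zero.

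| Handling | r = 0 | r = 0.2 | r = 0.3 |
|---|---|---|---|
| No reversion, no stop | 0.7/0.8 | 7/6 | 14/15 |
| Reversion only, 1.5x | 0.2/6 | 4/17 | 9/26 |
| Reversion and stop, 1.5x | 1-2/11 | 16/7 | 32/6 |
| Reversion and stop, 2x | 0-1/1-2 | 8-10/5-7 | 21-22/7 |

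The first row shows clustering alone: error rates inflate symmetrically once responses differ. At 1.5x, reversion alone leans against stimulation, and adding the stop turns the lean towards it when r is 0.2 or 0.3. With reversion and the stop, the pooled null median ratio is about 0.97-0.99 at r = 0.2 and 0.92-0.97 at r = 0.3.

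Sensitivity to the assumptions:
- Correlation of response with baseline, r = 0.2, 1.5x cut: at -0.5 (poor responders quick at baseline) about 7-9/16-17; at +0.5 about 28/3.
- The same at -0.5 with a 2x cut: about 9/9.
- Noisy 1.5x cut (log-SD 0.3): 0.4/19, 11/10 and 28/9 at r = 0, 0.2 and 0.3.

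**Step 3: one median per subject and condition, 10 v 10.** Power to detect a true ratio of 1.25, without stopping, session SD 0.4, r from 0 to 0.3:

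| Between-subject log-SD | 0.6 | 0.4 | 0.3 | 0.2 | 0.1 |
|---|---|---|---|---|---|
| Mann-Whitney | about 1% | 6-7% | about 17% | 20-49% | 38-91% |

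A signed-rank test on the same data has about 37-99%. That range follows r and does not depend on between-subject SD, because each subject's baseline cancels.

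**Step 4: the proposed estimator under the null.** Take the log of median stimulation time over median control time per subject, then the Hodges-Lehmann ratio. Across both cuts, session SD 0.4 or 0.6 and the noisy cut, the null ratio is 1.00-1.09, interval coverage is 90-96%, and a false finding of slower emptying occurs in about 3-9% of trials (nominal 2.5%).

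**The case against.** Several objections have force.

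- **Pooling is inferred.** Section 5.6 says the comparison is across subjects, which can mean subject summaries. The remark about many observations makes pooling plausible, no more. This stands, so the lean is conditional.
- **The direction is not fixed.** A reader might infer that the plan is biased towards stimulation. The documents do not support that. The lean needs pooled sessions and responses that differ between subjects. With identical response it runs against stimulation, and at r = 0.2 it vanishes or reverses under a negative correlation with baseline.
- **The 1.5x cut is severe.** It stops 5.7-6.2 of 10 subjects although stimulation is no worse on average, against 0.9-2.5 at 2x. Section 5.1 sets no threshold and allows nursing and clinical judgement.
- **Low power is not certain.** A reader might infer that a 10 v 10 unpaired test can almost never detect a 25% difference. That holds only at a between-subject log-SD of about 0.4 or more.
- **Dropped failures.** Excluding failed sessions would give much larger distortions, but nothing in the plan says they are excluded, and the outcome definition times sessions through to emptying. Such figures carry no weight here.
- **The remedy is not unbiased.** At 1.5x and r = 0.2 its null ratio (1.038) is further from 1 than the pooled one (0.974). It does better at r = 0.3.
- **Alternating subjects.** With 5 of 10 alternating, ending or continuing control sessions after an early stop barely matters: 12.8% v 15.1% favouring stimulation at r = 0.2, and 32.2% v 34.3% at r = 0.3. This is minor.

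The mismatch between a paired design and an unpaired test is untouched by any of these.

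**Conclusion.** The point holds, as something that should be fixed. Three facts rest on the text alone: own-control subjects meet an unpaired test, the unit of analysis is open, and stimulation data end after failures judged partly on the primary outcome, with no counterpart for control. The 3-against-21 imbalance follows by arithmetic from the rule and the stated schedule.

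The consequences rest on assumed inputs. Pooled sessions can give a biased comparison of uncertain direction, with a null ratio off by roughly 1-8% at the response SDs of 0.2 and 0.3 modelled. Subject summaries largely avoid that bias but give up the benefit of pairing, at a cost between slight and nearly total depending on how much subjects differ. Neither a definite bias towards stimulation nor a definite absence of power can be claimed. Confidence is medium. The clinical stopping rule is not in question.

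**What to change.** Change section 5.6 only, before data are seen:

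1. Replace the Mann-Whitney test with a within-subject analysis that weights subjects equally. For each subject take the log of median stimulation time over median control time. Apply the Wilcoxon signed-rank test across all analysed subjects, including any pooled from the other site, with site reported. Give the Hodges-Lehmann time ratio and its signed-rank interval as the effect size.
2. Keep every started stimulation session in the stimulation condition, timed by the existing definition through to emptying, fallback included. Log when stimulation ceased. Early-stopped subjects enter with the sessions they have.
3. Treat a session without emptying as censored at its last observed time and ranked longest. If a subject's stimulation median is then undefined, keep that subject in the signed-rank test at the most extreme rank against stimulation (against control if the control median is undefined). Report the affected limit of the ratio as not estimable where that follows. With 10 subjects the 95% upper limit is the 9th largest of 55 pairwise averages, and one infinite subject makes 10 of them infinite, so a single such subject is enough.
4. Report failures and early stops per subject, with a worst-rank sensitivity analysis for reverted sessions.

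The cost is wording and one log field. The downside is that the estimate measures stimulation plus fallback and is mildly conservative against stimulation, by the amounts in Step 4 of the working. If stimulation alone were 25% slower, it would read about 1.40-1.41 (1.5x cut) or 1.27-1.29 (2x cut) at session SD 0.4.

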5.2 Recruitment Methods

Patients of the SCI unit will be recruited by word of mouth by [name] at the SVAMC. As many patients will be recruited as needed to enroll 10 subjects into the study. Eligibility will be assessed via chart review and patient interview by the PI. Those expressing interest will be referred to study staff who will explain the study, highlight that it is voluntary, and answer any questions.

Every effort will be made to recruit individuals that are representative of the US population. The units treating patients with spinal cord injuries, stroke, or multiple sclerosis at the SVAMC have a particularly high proportion of subjects from underrepresented minority groups. The majority of individuals with neurogenic bowel dysfunction that are available for the study are male. Therefore it is expected that the majority of experiments will be performed on men. Every effort will be made to include women who should at least represent their prevalence in the spinal cord injured

population. All candidates will be treated the same with strict adherence to the inclusion and exclusion criteria.

Individuals who do not speak English will not be recruited. However, it is not anticipated that non-English speaking potential participants will be encountered.

Participants will be paid \$50 via check sent through the post upon completion or partial completion of the study.

5.3 Informed Consent Procedures

Informed consent will be obtained by a member of the research staff, after verbal explanation and provision of time for the subject to study the consent form and ask questions. The informed consent process will involve meeting with a potential subject in a quiet, private area (on the SCI Unit or in a physician's private office), finding out whether he or she is capable of giving consent, and discussing the purpose, risks, and benefits of participation. We will ensure that all subjects genuinely understand the study, that they are aware that participation is entirely voluntary, and that they can choose to discontinue participation at any time.

HIPAA authorization will be discussed with the potential participant at the time the patient is interviewed and a copy of the authorization will be given to them for their review. Specific information collected will include: Date of birth, date of spinal injury, level of spinal injury, gender, name, medical record number (social security number), current medications, previous bladder or urinary tract interventions, current medical status, and phone number. This information is being collected because these data are used to categorize individuals according to medical condition and allow investigation of medically related differences between the responses of different individuals. The participant's social security number will be collected in order to place appropriate documentation in the participant's medical record

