3.0 Objectives

This pilot study hopes to characterize the effects of minimally invasive electrical rectal stimulation on colonic motility in persons with neurogenic bowel dysfunction, as well as collect data to determine an effect size and so power future studies that measure colonic motility in response to electrical stimulation

Our hypothesis is that electrical rectal stimulation will produce increased colonic motility that results in defecation and that defecation time will be similar to subjects' typical bowel routines.

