5.5 Study Evaluations

Data collection will include standard medical charting and documenting outcome measures, such as bowel emptying time as written in section 5.6 Data Analysis. No tests, questionnaires, or procedures will be conducted beyond the typical bowel routine or stimulation testing described in this protocol.

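### Section 5.6 plans one unpaired test across subjects, so this own-control pilot estimates neither each subject's response nor how much the effect varies between subjects

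*Combined protocol and SAP*

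**What the plan says.** The abstract makes each subject their own control. Sections 3.0 and 5.6 say the pilot is to supply an effect size for powering later studies. The hypothesis in 3.0 is that "electrical rectal stimulation will produce increased colonic motility that results in defecation and that defecation time will be similar" to that of the usual routine; no margin is given.

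Section 5.3 lists the subject data: "Date of birth, date of spinal injury, level of spinal injury, gender, name", then medical record number, then "current medications, previous bladder or urinary tract interventions, current medical status, and phone number". It says these are used to categorise subjects by medical condition and to "allow investigation of medically related differences between the responses of different individuals".

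Section 5.6 names bowel emptying time as the primary outcome and gives one analysis, a Mann-Whitney rank-sum test at 0.05 to "compare bowel emptying times between typical bowel routines and electrical stimulation conditions" across subjects. It does not say whether the unit is the session or the subject. It has no per-subject estimate, no display by subject characteristics and no measure of how the effect varies.

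**The concern.** The rank-sum test treats the two conditions as independent samples and discards the pairing within subjects. Its p-value is not an effect size for planning an own-control study. That planning needs the mean within-subject effect and its between-subject SD, and 5.6 yields neither.

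Differing responses are plausible here. Section 5.4 admits multiple sclerosis, stroke and suprasacral spinal cord injury. Section 5.1 runs two schedules, divided at six months from injury, and ends a subject's stimulation period after three or more failures. If some subjects empty faster and others slower, one comparison across subjects can hide both. If the slower ones stop early, they contribute few stimulation sessions and the pooled comparison shifts towards stimulation.

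**Working it through.** **The plan's own figure.** The sample size is 10. No effect size, SD, power or margin is given, so there is no calculation to reproduce.

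**Inputs from the documents.** Ten subjects, six weeks per period, and a routine every other day give 42/2 = 21 sessions per condition. At 3 to 5 sessions a week the range is 6×3 = 18 to 6×5 = 30. Subjects under six months from injury alternate conditions, so 21 each does not apply to them generally.

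**Assumptions, not in the documents.** Log-normal times with median 60 minutes, independent sessions, between-subject log-SD 0.3–0.6 and within-subject log-SD 0.3–0.5. Each subject's true time ratio is ×1.25 or ×1.5, or its inverse. Tests are two-sided at 0.05, with 600 simulated trials per scenario.

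**Even split, full follow-up.** With five slower and five faster, the session-pooled test rejects in 0.2–3.2% of trials. On average 2.8 to 9.9 of the ten subjects nevertheless differ at p<0.05 in their own data.

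**Other splits and early stopping** (ratio ×1.5, except in the no-effect row; 21 sessions, both log-SDs 0.4):

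| Scenario | Pooled test rejects | Rejects with stimulation faster |
|---|---|---|
| No effect | 1.3% | 0.5% |
| 5 slower, 5 faster | 0.8% | 0.7% |
| 4 slower, 6 faster | 23% | 23% |
| 6 slower, 4 faster | 23% | 0% |
| 3 slower, 7 faster | 90% | 90% |
| 7 slower, 3 faster | 86% | 0% |
| 5 slower, each stopping after 3 stimulation sessions | 95% | 95% |
| 7 slower, each stopping after 3 stimulation sessions | 68% | 67% |

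With subject means as the unit (10 against 10, still unpaired), the test rejects in at most 0.5% of trials in every scenario.

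**Why early stopping tilts the pooled result.** Five slower subjects stopping after 3 sessions supply 5×3 = 15 of 15+105 = 120 stimulation sessions (12.5%), but 105 of 210 control sessions (50%). With seven, the shares are 21 of 84 (25%) and 147 of 210 (70%).

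**What subject-level estimates would show.** Take true log ratios of ±0.3 (exp(0.3) = 1.35, exp(−0.3) = 0.74) and within-subject log-SD 0.4–0.6.

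- Standard error of one subject's log ratio: SD×√(2/21) = 0.123 to 0.185. With t = 2.021 on 40 df, the 95% interval is ×/÷ exp(0.249) = 1.28 to exp(0.374) = 1.45. A subject at 1.35 has an interval of 1.05–1.73 in the first case and 0.93–1.96 in the second.
- If that subject stopped after 3 stimulation sessions: SD×√(1/21+1/3) = 0.247 to 0.370. With t = 2.074 on 22 df, the interval is ×/÷ 1.67 to 2.16.
- SD of the ten true effects at an even split: √(10×0.09/9) = 0.316. Adding session noise gives an observed SD of √(0.100+0.015) = 0.339 to √(0.100+0.034) = 0.366. With no true variation it would be about 0.123 to 0.185.
- Interval for the mean effect: 2.262×0.339/√10 = 0.243 to 2.262×0.366/√10 = 0.262, so ×/÷ 1.27 to 1.30 around a mean ratio of 1.

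At an even split the paired mean is therefore also null. The plot and the SD reveal the disagreement.

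**The case against.** Several stronger readings are tempting, and the documents do not support them.

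- *The plan promises to explain why individuals differ.* It does not. The 5.3 sentence justifies data collection in the authorisation, and neither 3.0 nor 5.6 lists such an aim.
- *Opposite responses would be reported as similar.* Section 5.6 has no rule that turns a non-significant result into similarity; a reader would have to make that step. The missing margin is a separate weakness.
- *Masking is certain.* An even split with equal and opposite effects is the worst case. At 3:7 the pooled test rejects in 31–70% of trials with log ratios of ±0.3, and in 86–90% at ×1.5. The three-failure trigger leaves room for judgement. If failure is taken as a session above the subject's own 75th, 90th or 95th control percentile, pooled rejection at an even split is roughly 10–66%, nearly always with stimulation looking faster.
- *Bowel information is absent because 5.3 asks about the bladder.* The list does name "previous bladder or urinary tract interventions" and no bowel counterpart. But section 5.1 says "Nurses will log dig stim data as they usually do and this data will be used as control data for the study", and 5.5 says "Data collection will include standard medical charting and documenting outcome measures, such as bowel emptying time". Significant colon trauma and colostomy are excluded in 5.4. The bladder item plays no part in the masking, which comes from the single test.

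A heterogeneity test is also an unsafe remedy. It has about 6% false positives with independent sessions, but about 27% and 44% at lag-1 autocorrelation of 0.2 and 0.3, and 19–36% with subject-specific period drift of SD 0.1 log units. With ten subjects, any breakdown by diagnosis is descriptive.

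All of this stands, and it limits the point. It does not answer the central gap: an own-control pilot run for an effect size has no within-subject estimate in its plan.

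**Conclusion.** The concern holds in a limited form. As written, 5.6 cannot deliver the within-subject effect or its variation, and it gives no analysis for the use of subject data stated in 5.3. That conclusion rests on the text alone.

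The possible consequences rest on assumed variances, effects and independent sessions. With a near-even split and full follow-up, the test could show no difference (rejection at most about 3%). With a less even split, the pooled result can follow the majority. With early stopping it can favour stimulation even when most subjects are slower: 67% of trials with seven of ten slower, if each stops after three stimulation sessions. None of these outcomes can be called likely from the documents. The 5.3 list is a minor matter of wording.

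**What to change.** Replace the single comparison in 5.6 with wording to this effect:

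> For each subject we will estimate the ratio of emptying time on stimulation to that subject's own control sessions (or the median shift), with a 95% interval. The subject is the unit of analysis. The ten estimates will be shown in one plot, arranged by diagnosis, injury level and schedule, with subjects whose stimulation period ended early marked. We will report the mean within-subject effect with its 95% interval and its between-subject SD. Similarity will not be concluded from a non-significant average alone. Subject-level results are descriptive.

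Note beside the SD that the observed value includes session-to-session noise. Do not make any conclusion depend on a heterogeneity test.

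As a secondary change, add previous bowel or anorectal interventions to the data list and authorisation text in 5.3, preferably before enrolment so that the item need not be recovered later.

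The cost is a paragraph of analysis wording, one plot and one line in the data list. The downside is that single-subject intervals are wide, particularly for early stoppers, and in fixed-order subjects they contain any period effect.
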